#### **Data and Statistical Analysis**

We will calculate the root mean square (RMS) amplitude of the evoked response, the RMS amplitude of the pre-stimulus background EMG (over a duration of approximately 25 ms matched to the

duration of the corresponding evoked response), and the peak-to-peak amplitude of the evoked response (MEP or M-wave) using purpose-written Matlab code (The MathWorks, Inc.). Stimulus events where the pre-stimulus RMS amplitude is larger than the evoked response, or where voluntary activity is detected, will be discarded to ensure similar levels of background activity across subjects and trials. MEP amplitudes will be normalized by their corresponding Mmax amplitudes. All patient characteristics, including RMTs and AMTs, will be summarized using means and standard deviations. The overall mean and standard deviation of MEPs (normalized to Mmax and unnormalized) will be reported. Linear mixed effect models will be used to determine the overall mean difference between the normalized MEP amplitudes between the active and sham protocols. Separate mixed effect model analyses will be used for each muscle (biceps and FDI), condition (sham and active) and time point following iTBS (in total 12 mixed effect models). Since this is a pilot study, all inference will be performed at the 0.25 level and no adjustment for multiple comparisons will be made. Pearson correlation coefficients will be computed to test for correlations between mean MEPs in response to single pulse TMS (before iTBS protocol) and the maximum induced electric field. A strong correlation between MEPs and induced electric fields would indicate a strong relationship between our experimental and computational outcome measures and provide a foundation for our future work. Pearson correlation coefficients will also be computed to test for correlations between mean MEPs following iTBS and maximum induced electric fields to determine whether greater induced electric fields indicate a participant is more responsive to the iTBS protocol.

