### ***Biostatistical Justification***

The difference in the corticomotor excitability (as measured by the amplitude of the motor evoked potentials (MEPs)) can be used to determine if there is a difference between the active and sham protocols. Under the conditions that the true difference between the active and sham protocols is 5% of the normalized MEP with a standard deviation of 9%, and that the correlation between the differences within an individual is 0.5, ten nonimpaired subjects will be needed to achieve at least 80% power using a two-sided test of the overall mean using a repeated measures model. The Type-I error rate was set at 0.25 for this analysis.

In our **future research**, we will design neuromodulation techniques that promote neuroplasticity to increase muscle strength and function in individuals with SCI or post-stroke. The goal of our larger project, to be submitted as an R01 application to National Center for Medical Rehabilitation Research (NCMRR) within the Eunice Kennedy Shriver National Institute for Child Health and Human Development (NICHD) in June 2020, is to determine the effect of neuroanatomy and intermittent theta burst stimulation on corticomotor excitability, and clinical scores of function in individuals with tetraplegia. This larger project will include development of a computational framework to model hysteretic effects of iTBS using participant specific MRI in order to more definitely determine the effect of brain anatomy on the efficacy of iTBS. This larger project aligns with two research priorities within NCMRR: 1) to explore multimodal approaches that promote plasticity and sensorimotor function, particularly the combination of physical therapy with stimulation treatments, and 2) to develop objective measures that may predict rehabilitation treatment response, monitor functional progress, and tailor interventions to the individual abilities, needs, and resources of the person with disabilities.

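### The sample size rests on one overall active-sham test at 0.25, but the analysis splits it by muscle, condition and time, all at 0.25, and names no deciding test

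*Combined protocol and SAP*

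**What the plan says.** All references are to the combined protocol and SAP.

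- **Biostatistical Justification.** Ten participants are said to give at least 80% power for a true active-sham difference of 5% of normalized MEP, with SD 9% and within-person correlation of the differences 0.5. The test is "a two-sided test of the overall mean using a repeated measures model", and "The Type-I error rate was set at 0.25 for this analysis".
- **Data and Statistical Analysis.** Linear mixed models are introduced as the way to estimate the overall active-sham difference. The next sentence divides the work by muscle, by stimulation type, and finally by "time point following iTBS (in total 12 mixed effect models"). The inference rule opens with its reason, "Since this is a pilot study", and continues "all inference will be performed at the 0.25 level and no adjustment for multiple comparisons will be made".
- **Transcranial Magnetic Stimulation in Human Subjects.** MEPs are recorded before iTBS and 10, 20 and 30 minutes after it, with one session for the biceps and one for the FDI.

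Neither statistical section labels a test, muscle or time point as primary.

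**The concern.** The two sections describe different analyses. The error rate and power belong to a single overall test, and that test is not among the listed models. The listed models break the result up by muscle and time, and each is read at 0.25. Nothing says which result answers the active-versus-sham question, so a positive conclusion could rest on any one of several 25%-level tests. The 0.25 and the 80% in the sample-size section would then not describe the conclusion actually drawn. This matters because the study is meant to inform a larger project.

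**Working it through.** **Inputs from the documents:** n = 10; difference 5; SD 9; correlation 0.5; two-sided level 0.25; two muscles; three post-iTBS times.

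**Assumptions of this check:** SD 9 is the SD of one active-sham difference. The repeated measures are the three times in one muscle. Tests are one-sample t-tests on within-person differences (df 9, critical value 1.230).

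**1. Reproduce the stated sample size.**
- Variance of a person's mean over m differences = SD² × (1 + (m − 1)ρ)/m.
- With m = 3: 81 × (1 + 2 × 0.5)/3 = 54, so the SD is 7.35.
- Noncentrality = 5 × √10/7.35 = 2.15, giving power 0.82.
- With n = 9 the power is 0.79, so ten is the smallest n that reaches 80%.
- This reading is not unique. With m = 2, power at n = 10 is 0.79 by the t-test and 0.81 by the normal approximation. With m = 6 and all correlations 0.5 it is 0.86.

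**2. Power of a single time-point contrast.** The variance is 81, and the noncentrality is 5 × √10/9 = 1.76. Power is 0.71, and 14 people would be needed for 80%.

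**3. Chance of at least one p<0.25 across six active-sham contrasts (2 muscles × 3 times), no true effect.** If the contrasts were independent it would be 1 − 0.75⁶ = 0.82. Simulation with n = 10 and 60,000 runs per row gives:

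| Correlation across times | Correlation between muscles | Chance of at least one p<0.25 |
|---|---|---|
| 0.5 | 0 | 77% |
| 0.5 | 0.5 | 72% |
| 0.8 | 0 | 67% |
| 0.8 | 0.5 | 63% |
| 0.9 | 0 | 61% |
| 0.9 | 0.5 | 57% |

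Only the 0.5 comes from the plan, and applying it to every pair of contrasts is an assumption. The values 0.8 and 0.9, and every between-muscle value, are also assumed. In the extreme case of 0.9 between all six contrasts the figure is 45%.

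**4. Power of a single decision test.**
- One muscle, averaged over three times: 0.82, from step 1.
- Both muscles, averaged over six differences, with between-muscle correlation g: variance = 81 × (12 + 18g)/36 = 2.25 × (12 + 18g). This is 27 at g = 0 and 47.25 at g = 0.5.
- If both muscles have the 5% effect, power is 0.96 (g = 0) to 0.86 (g = 0.5).
- If only one muscle responds, the average effect is 5/2 = 2.5%, and power is 0.63 (g = 0) to 0.49 (g = 0.5).

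**The case against.** The plan is open about what it does. It gives pilot status as the reason for 0.25 and for making no adjustment, and it nowhere claims that 25% holds across the family of tests. Whether a ten-person pilot needs family-wise control is partly a matter of judgement. The sample-size section also ties the active-sham question to one overall test, and the analysis section mentions the overall difference before splitting it. The central hypothesis, moreover, concerns anatomy and induced electric fields, which are examined by Pearson correlations, so active versus sham is not the only question.

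Most of this stands. It removes any complaint about 0.25 as such, and any claim that the plan misstates a family-wise rate or contains no overall test. It does not remove the mismatch: the powered test is not among the listed models and is not named as deciding.

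A reader might go further and apply the 0.25 level to all 12 models, getting 1 − 0.75¹² = 97% if they are independent, and conclude that the trial would almost always find an iTBS effect. The documents do not support that. The models are split by condition, so none can estimate active minus sham, and six hold sham data only. The plan does not say what hypothesis each one tests. No false-positive rate for iTBS should be drawn from the 12.

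**Conclusion.** The concern holds as a mismatch between the powered test and the listed analyses, with no deciding test named. For the six active-sham contrasts, the chance of at least one p<0.25 without any effect is about 72-77% at the plan's correlation of 0.5. It is about 57-67% at assumed correlations across times of 0.8-0.9 and between muscles of 0-0.5. These are ranges under assumptions, and neither lower end is a floor, but every case examined is well above 25%. The stated 80% power also does not carry over to a single time-point contrast, which has 0.71.

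A reader might infer that the study's only formal answer is unreliable. That goes too far: an overall test at 0.25 with adequate power is already in the plan and only has to be named.

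**What to change.** State in Data and Statistical Analysis that the decision test at 0.25 is the one in the Biostatistical Justification: a repeated-measures active-sham difference averaged over 10, 20 and 30 minutes, in one muscle named in advance as primary. This keeps the error at 0.25, the sample at ten and the power at 0.82.

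An alternative is to average over both muscles. That changes the estimand, because the plan otherwise treats biceps and FDI separately, with their own sessions and hotspots. Power is then 0.86-0.96 if both muscles have the 5% effect, but only 0.49-0.63 if one does. The choice should be stated together with that trade-off.

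Report all other muscle and time results as exploratory estimates with confidence intervals, without significance claims. The cost is SAP wording only, with no new data. The downside is that muscle-specific and time-specific results become secondary.

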## Approach

Our central hypothesis is that brain anatomy impacts the efficacy of iTBS therapy. The basis for this hypothesis is that anatomical complexities of cortical motor regions and their corresponding fiber tracts determine TMS induced electric fields in the brain, and these electric fields are the mechanistic drivers of TMS-based therapies. The rationale for our proposed research is that elucidating the impact of brain anatomy on the efficacy of iTBS is beneficial for two primary reasons: 1) imaging techniques provide the opportunity to identify the best patients for iTBS therapy based on their brain anatomy, and 2) stimulation therapy could be optimized based on the patient's brain anatomy. Thus, the effect of brain anatomy on iTBS efficacy is important to tailor rehabilitation appropriately.

In order to determine the effect of brain anatomy on the induced electric fields acting on cortical neural fiber tracts projecting to upper limb muscles from single pulse TMS we will create anatomically accurate computational brain models using MR images from ten nonimpaired individuals. The brain models we develop will incorporate anatomical features, including fiber tracts, from magnetic resonance imaging (MRI) data we record from these ten nonimpaired participants. We will record neurophysiologic data from the same ten nonimpaired participants in order to test for correlations between biceps and FDI motor evoked potentials before and following iTBS with modeled induced electric fields acting on their corresponding cortical fiber tracts.

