## Computational Brain Modeling and Simulation of TMS

We will use MRI data from ten nonimpaired individuals to create 3D head and brain models of each individual. Using the software Freesurfer, along with high-resolution T1 and T2 weighted images, we will create high-resolution anatomically accurate models with differentiated skin, bones, cerebrospinal fluid, grey matter, white matter, and ventricles within the brain. The Freesurfer software we will use is open-source and developed for analyzing MRI images for development of 3D models. We will input MRI slices and use contrast information to estimate anatomical boundaries, such as that between the skin and skull, or between grey matter and white matter. A 3D mesh is then created using these estimated boundaries and other geometrical information taken directly from the input MRI data.

We will use high resolution DTI data and extract fiber tracts using a graphical toolbox ExploreDTI. Fiber tracts are constructed using whole brain tractography. Tracts will be drawn from a seed region of interest, such as M1, with seed fractional anisotropy threshold of 0.2, minimum fiber length of 50 mm and angle threshold of 30 degrees. Coordinates of tracts are imported into SolidWorks and

extruded to a solid, 3D line. These 3D fiber models are exported as .STL files for finite element analysis in Sim4Life. Figure 3 shows on the left the fiber tracts originating from M1, and on the right fibers being stimulated by a figure-of-eight TMS coil. The fiber models will be embedded into our 3D head models to calculate the induced electric field during TMS in different regions of the brain.

**Fig. 3.** M1 fibers will be extracted from DTI MRI. Isolated fiber tracts will be exported as 3D objects in order to simulate the induced electric field from TMS on the 3D fibers at regions of interest in the brain.

Using finite element analysis, we will determine the induced electric fields acting on isolated fiber tracts by simulating TMS in Sim4Life software. We will specify material properties (see Table 2), grid details, and the current source, similar to our previous work. Induced electric fields will be calculated using the Slice Viewer and Surface Viewer utilities within Sim4Life. Voxels stimulated above a threshold electric field of 150 V/m will be recorded.

**Table 2.** Material properties we will specify in Sim4Life simulations of TMS.

Structure	Mass Density ( $kg/m^3$ )	Electric Conductivity (S/m)

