### **Transcranial Magnetic Stimulation in Human Subjects**

Subjects who underwent MR imaging, will also participate in two sessions of TMS. Each TMS session will consist of baseline measures of MEPs in response to single pulse TMS, followed by the iTBS protocol. One iTBS session will target the biceps, and one session will target the FDI. Each session will consist of active iTBS applied to the hotspot of the target muscle, and sham iTBS. Sessions will be separated by at least 3 days to minimize the potential for carry over effects. Before and 10, 20 and 30 minutes after each iTBS session, MEPs will be recorded in order to quantify corticomotor excitability similar to our preliminary work.

Subjects will be instrumented with surface electromyography (EMG) electrodes on their dominant arm after the skin is shaved and cleaned with alcohol wipes. Surface EMG electrodes (disposable Ag-AgCl, Noraxon) will be located over the biceps and the FDI. EMG signals will be amplified (x1000) and bandpass-filtered prior to A/D conversion (CED Micro 1401 MkII, Cambridge Electronic Design). All EMG data will be sampled at 2 kHz using Spike2 software (Cambridge Electronic Design) and stored on a personal computer for offline analysis.

Prior to the iTBS session, the maximal compound muscle action potential (Mmax) will be recorded from the target muscle (biceps or FDI). The amplitude of Mmax is required to normalize MEP amplitudes.

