To record Mmax, single pulse electrical stimuli, 0.2 ms pulse width will be delivered to Erb's point via a bipolar stimulating electrode (0.47 cm^2; 2.5 cm inter-electrode distance) connected to a constant current stimulator (DS7AH, Digitimer Ltd.). To determine RMTs and record MEPs, single pulse TMS will be delivered to the motor cortex contralateral to the resting target arm using a Super Rapid Plus stimulator via a 70 mm figure-of-eight coil. The vertex at the intersection of the inion-nasion and inter-aural lines will be marked on a linen cap tied snugly on the subject's head. The coil will be held tangentially on the scalp via a support stand with the coil center rotated to induce a posterior-to-anterior cortical current across the central sulcus. The hotspot for the target muscle will be identified as the location evoking the largest peak-to-peak amplitude MEP using the lowest stimulation intensity. Resting motor threshold (RMT) will be determined as the lowest stimulus intensity that induces MEPs of  $\geq 50 \mu\text{V}$  in at least 5 of 10 consecutive stimuli with the target muscle fully relaxed. The stimulus intensity for ensuing single pulse MEP trials will be set at 120% of RMT. To record MEPs, the stimulator will be triggered to deliver 15 stimuli at a rate of 0.2 Hz. Active motor threshold (AMT) will then be determined during sustained contractions of 20% the subject's maximum effort. With visual feedback provided relative to their maximum EMG root mean squared value, subjects will sustain a 20% maximum effort contraction of the target muscle during which AMT will be determined as the stimulus intensity that elicits a MEP  $\geq 200 \mu\text{V}$  in at least 5 of 10 consecutive stimuli.

**Fig. 4.** The biceps and FDI will be targeted for the iTBS protocol in nonimpaired subjects. All subjects will be seated with the arm supported against gravity in the horizontal plane. The intensity of all iTBS pulses will be 80% of the subject's active motor threshold (AMT). Before each iTBS session (iTBS 1 and 2, which are sham and active, respectively), RMTs and motor evoked potentials (MEPs) will be recorded. MEPs will also be recorded at 10 minute intervals following iTBS.

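### The test of responsiveness to iTBS correlates the electric field with the post-iTBS MEP level, which is not a measure of response

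*Combined protocol and SAP*

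**What the plan says.** The Approach section opens with the aim: "Our central hypothesis is that brain anatomy impacts the efficacy of iTBS therapy". The Data and Statistical Analysis section then plans two sets of Pearson correlations with the maximum induced electric field.

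- The first uses the mean MEP before iTBS. It serves as a check of the model: "A strong correlation between MEPs and induced electric fields would indicate a strong relationship between our experimental and computational outcome measures".
- The second uses the MEP after iTBS: "Pearson correlation coefficients will also be computed to test for correlations between mean MEPs following iTBS and maximum induced electric fields". Its purpose is "to determine whether greater induced electric fields indicate a participant is more responsive to the iTBS protocol".

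MEPs are normalized to Mmax, which is recorded before the iTBS session. Baseline MEPs exist. Under Transcranial Magnetic Stimulation in Human Subjects the plan says "Before and 10, 20 and 30 minutes after each iTBS session, MEPs will be recorded", and the Fig. 4 legend adds "Before each iTBS session (iTBS 1 and 2, which are sham and active, respectively), RMTs and motor evoked potentials (MEPs) will be recorded". Each block, sham and active, therefore has its own pre-iTBS value, but the second correlation does not use it. That legend also calls both blocks iTBS, so the phrase about MEPs following iTBS does not strictly say that only the active block is meant.

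**The concern.** Responsiveness is a change produced by the stimulation. The planned outcome is a level, which still carries each person's starting excitability. Dividing by Mmax scales for the muscle's maximal response and leaves differences in baseline corticomotor excitability in place.

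Two harms follow. First, if the field is related to baseline MEP, the post-iTBS correlation partly repeats the baseline one, and a participant with larger MEPs to begin with can be read as a better responder. The plan tests for that relation and would welcome it, so a successful model check would contaminate the responsiveness test. Second, even if field and baseline are unrelated, baseline variation acts as noise and reduces power to detect a true relation between field and change.

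This is the only planned analysis that links the modelled field to iTBS response. The mixed models compare active with sham and do not mention the field.

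**Working it through.** **Inputs from the plan.** n = 10 and two-sided testing (Biostatistical Justification); alpha 0.25 without multiplicity adjustment (Data and Statistical Analysis). The plan's only sample-size figure concerns active against sham. It reproduces if the overall mean averages three post-iTBS time points: SD = 9 × √((1 + 2 × 0.5)/3) = 7.35, and with a difference of 5 and n = 10 the t-test has 82.2% power. It has no bearing on the correlations, for which no power is stated.

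**Assumed inputs.** Every correlation below. The documents fix neither the size nor the sign of r(field, baseline). Test pulses are set at 120% of each person's RMT, and the simulated current is described only by reference to earlier work ("grid details, and the current source, similar to our previous work").

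**Critical values.** |r| = t/√(df + t²). Pearson, 8 df, t = 1.240: 0.402. Partial correlation on baseline, 7 df, t = 1.254: 0.428.

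The rates below come from simulation with 200,000 runs per cell.

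**1. No true relation of field to response; change independent of baseline and field.** Then r(field, post) = r(field, baseline) × r(baseline, post).

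| r(field, baseline) / r(baseline, post) | implied r(field, post) | post level rejects | partial or change rejects |
|---|---|---|---|
| 0 / any | 0 | 25% | 25% |
| 0.3 / 0.5 | 0.15 | 29.5% | 25% |
| 0.5 / 0.7 | 0.35 | 47% | 25% |
| 0.7 / 0.9 (extreme) | 0.63 | 84% | 25% |

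**2. Power with r(field, change) = 0.6 and r(field, baseline) = 0.** Then r(field, post) = 0.6 × √(1 − r(baseline, post)²).

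| r(baseline, post) | implied r(field, post) | post level | partial | active change |
|---|---|---|---|---|
| 0.5 | 0.52 | 70% | 77% | 80% |
| 0.7 | 0.43 | 57% | 77% | 80% |
| 0.9 | 0.26 | 38% | 77% | 80% |

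For active-minus-sham change, r = 0.6/√(1 + k²), where k is the SD of sham change over the SD of active change and the two are independent. For k = 0.5, 0.75 and 1.0, r = 0.54, 0.48 and 0.42, and power is 72%, 64% and 57%.

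**3. Limits of the alternatives, again with no true relation.**

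- *Noisy baseline* (pre and post share one true level plus independent error; r(field, observed baseline) = 0.3/0.5/0.7 with reliability 0.5/0.7/0.9): post level 42/67/91%, partial 31/35/34%, change score 25%.
- *Regression to the mean* (equal variances, post independent of field given baseline; pairs 0.3/0.5, 0.5/0.7, 0.7/0.9): change score 29/32/30% with a spurious negative correlation, partial 25%.

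**4. Reading the two planned correlations together.** With no response relation (0.5/0.7), both are significant in 41% of trials, and post alone in about 47% − 41%, or nearly 7% before rounding. With a relation to change only, as in step 2, the pattern of post significant and baseline not significant appears in just 53%, 43% and 23% of trials.

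**The case against.** The strongest reply has four parts.

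1. *The false-positive harm rests on an unknown.* Setting pulses at 120% of each person's RMT may already absorb part of the between-person difference in field. With no field-baseline relation the test holds its level, and at the mildest pairing it rejects only 29.5%. This stands: the larger figures are illustrations and should not set the severity.

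2. *The baseline correlation is planned too, so a reader would be warned.* In the 0.5/0.7 case, about 86% of the misleading post-iTBS results (41/47.4) come with a significant baseline correlation. This stands in part. However, the plan specifies no comparison, and finding both significant cannot separate a carried-over baseline relation from a true response. The joint reading also has poor sensitivity to a real one.

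3. *The choice of remedy is debatable.* The change score holds its level with noisy baselines, where partial correlation does not, and has slightly more power in step 2. This stands, and is why both should be reported. It does not rescue the post-iTBS level.

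4. *This is a pilot.* The Approach section speaks only of correlating MEPs before and following iTBS with the field, and the firmer answer is left to a larger project. Even so, the analysis section attaches a specific inference about responsiveness to this test, and a lenient alpha does not repair a mismatch between outcome and question. The uncertainty over sham and active is minor, since responsiveness most naturally refers to active stimulation.

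**Conclusion.** The concern holds. As written, the analysis does not answer the question the plan sets for it. The mismatch needs no assumption; it follows from the plan's wording. Its numerical effect does depend on assumptions. The false-positive rate ranges from the nominal 25%, if field and baseline MEP are unrelated, through 29.5% and 47% to 84% in an extreme case. The loss of power needs no field-baseline relation, but its size depends on how strongly baseline and post-iTBS MEPs correlate. This should be fixed: it affects the one analysis that bears on the central hypothesis, and it can be corrected before analysis with data already planned.

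**What to change.** Amend the Data and Statistical Analysis section as follows, for each muscle.

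- **Responsiveness analysis:** partial correlation of the maximum field with the normalized MEP after active iTBS (mean of 10, 20 and 30 minutes), adjusted for the pre-iTBS MEP of that same block.
- **Supporting analyses:** correlation of the field with the active change from baseline, and with the active-minus-sham change.
- **Descriptive only:** the raw post-iTBS correlation, shown beside the baseline correlation and not interpreted as response.
- **Wording:** state that the active block is meant.

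No new data are needed. The partial correlation costs one degree of freedom. It leaves some confounding if baseline MEPs are noisy, while the change score is exposed to regression to the mean. Subtracting sham change adds noise and can lower power to that of the post-level test (57%). No single measure is safe in every case, so the supporting results should be reported whatever the first one shows.
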